13.3 Unsolicited Adverse Events

This analysis applies to all ongoing solicited AEs beyond seven days after the vaccination, all unsolicited AE's occurring during the study, judged either as probably related, possibly related, or not related to vaccination by the investigator, recorded in the AE eCRF, with a start date on (but with onset after vaccination) or after the date of vaccination. AE starting prior to study vaccination will only be listed.

The original verbatim terms used by investigators to identify AEs in the eCRFs will be mapped to PTs using the MedDRA dictionary.

The AEs will then be grouped by MedDRA PTs into frequency tables according to SOC. All reported AEs, as well as AEs judged by the investigator as at least possibly related to study vaccine, will be summarized according to SOC and the PT within SOC. These summaries will be presented by the vaccination group. When an AE occurs more than once for a subject, the maximal severity and strongest relationship to the vaccine group will be counted.

The assignment to time intervals will be done by day of onset and not by days ongoing/persisting.

Statistical Analysis Plan, Protocol Number V87_30

06 MAY 2022 Final Version 1.0

The summaries will be presented by SOC and PT and different periods of onset depending on the category of events.

- From Day 1 to 21 days after the last vaccination:

- AE
- AE by maximum severity
- Related (i.e. at least possible) AE
- SAEs
- Related SAEs
- AESIs
- NOCD
- AEs leading to withdrawal (from the study or the second vaccination)
- Deaths.

- From Day 1 to end of study:

- SAEs
- Related SAEs
- AESIs
- NOCD
- AEs leading to withdrawal (from the study or the second vaccination)
- Deaths.

A summary of subjects with solicited and unsolicited non-serious treatment emergent adverse events reported by >5% of subjects sorted by system organ class and preferred term will be provided for clinicaltrials.gov and EudraCT.eu posting purposes.

Data listings of all AEs will be provided by the subject. In addition, AEs in the categories above will be provided as listed data.

Statistical Analysis Plan, Protocol Number V87_30

06 MAY 2022 Final Version 1.0

All tables will be produced overall and by age subgroup. The overview summary as well as the summary of AEs and SAEs will be also be presented by the other subgroups.

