8.1 Endpoints

8.1.1 Primary Endpoint(s)

8.1.1.1 Primary Safety Endpoint(s)

The measures for assessing safety and reactogenicity are as follows:

- Percentages of subjects with solicited local and systemic AEs¹⁰ that occur within 7 days following each vaccination and calculated for 4 time intervals after vaccination: 30 minutes, 1 through 3 days, 4 through 7 days, and 1 through 7 days.
- Percentages of subjects with any unsolicited AEs reported within 21 days after each vaccination within each vaccine group.
- Percentages of subjects reporting SAEs, NOCDs, AESIs, and AEs leading to vaccine and/or study withdrawal, as collected from Day 1 through Day 387.

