- **Pre-vaccination (will be mapped to MH):** start date before the date of first injection of study vaccine or indicated as on injection day but before injection.
- **Emergence during vaccination phase:** all other cases.

Note: If an AE start date is missing or unknown and no indication is provided on the timing, the AE will be considered as emergent.

When start and/or end dates of an AE are only partially known, AEs will be categorized as emergent before, during, or after vaccination phase using the following rules:

- If the partial end date is before ($<$) the first vaccination (i.e., year or year & month is/are before the study vaccination year or year & month) then the AE is pre-vaccination.
- If the partial start date is equal or after (\geq) the first study vaccination (i.e., year or year & month is/are after or the same as the first study injection year or year & month) then the AE is emergent during vaccination phase.

Statistical Analysis Plan, Protocol Number V87_30

06 MAY 2022 Final Version 1.0

All AEs emergent during vaccination phase will categorized as occurring during the period of 21 days following the last vaccination based on the start date. If start date is missing or incomplete, events will be counted as yes during the period of 21 days following the last vaccination.

Adverse events that meet none of the following criteria SAE, AESI, NOCD, or AE leading to withdrawal, and had a start date more than 21 days after the last vaccination are not to be recorded. However, if recorded, these AEs should be flagged (**i.e. exclusion flag**), excluded from analysis and listed separately.

The **maximum event severity** is the greatest severity associated with a preferred term (PT) for a reported AE according to the following order: Mild < Moderate < Severe.

Vaccination-related Adverse Events are those for which the cause has been evaluated by the investigator, and recorded as possibly related, probably related or unknown/ missing.

Prior and Concomitant Medications

All medications will be characterized according to the start and end date of occurrence related to the vaccination as follows:

- **Pre-vaccination:** start date before the date of first injection of study vaccine.
- **Concomitant:** start date before vaccination but continued after vaccination or start date after vaccination. The period Day 1- 43 (i.e. 21 days after the last study vaccination) will be labeled if the start date is on or before Day 43.

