| | | Arthralgia | No interference with daily activity | Interferes with daily activity | Prevents daily activity |
| | | Headache | No interference with daily activity | Interferes with daily activity | Prevents daily activity |
| | | Malaise | No interference with daily activity | Interferes with daily activity | Prevents daily activity |
| Overall | | Shivering/Chills | No interference with daily activity | Interferes with daily activity | Prevents daily activity |
| Overall | | Fever | 38.0 - 38.9 °C | 39 – 39.9 °C | ≥40.0 °C |

Note: presence of an event on a day is defined as mild, moderate or severe; absence is defined as none. Ecchymosis, Erythema and Induration: grading will be derived from the actual measurements in mm; Fever will be derived from the actual measured body temperature.

Statistical Analysis Plan, Protocol Number V87_30

06 MAY 2022 Final Version 1.0

Other Indicators of Reactogenicity

The use of analgesics/antipyretics will be captured as “absent” or “present” separately by reason “for treatment” or “for prevention”.

The analyses will encompass various summaries of the data by vaccination and – where applicable - combined across the two vaccinations using the solicited safety set:

1. Overall summary of subjects with solicited AEs
2. Solicited local AEs, maximum event severity by event and interval
3. Solicited systemic AEs, maximum event severity by event and interval
4. Number of days of solicited AEs, including ongoing AE after Day 7
5. Daily reports of subjects with solicited AEs, only per vaccination
6. Day of first onset of solicited AEs, only per vaccination
7. Solicited AEs ongoing at Day 7
8. Distribution of maximum temperature
9. Other use of analgesics/antipyretics

For each of the time points or time intervals presented in the summaries, only subjects with at least one valid observation (i.e., any non-missing values but excluding “Not done/unknown” and implausible values) for the solicited adverse events in the interval of interest will be considered. Subjects without valid data will be removed from the denominator to prevent a downward bias (towards zero).

All tables are run by age stratum and vaccine group. The local solicited AEs and the common systemic solicited AEs (as defined in Table 3) are also presented combining the two age strata.

Overall summary of subjects with solicited adverse events.

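### The SAP summarises unsolicited adverse events over one pooled window only, although the protocol's primary safety endpoint is framed for each vaccination

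*SAP*

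**What the plan says.** Protocol 8.1.1.1, with matching text in the synopsis, lists this among the primary safety endpoints: "Percentages of subjects with any unsolicited AEs reported within 21 days after each vaccination within each vaccine group".

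SAP 13.3 sets two onset periods for unsolicited events:

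- All adverse events, events by maximum severity and related events are summarised only for "From Day 1 to 21 days after the last vaccination".
- The other period, "From Day 1 to end of study", is limited to serious events, related serious events, events of special interest, new chronic disease, withdrawals and deaths.

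SAP 8.7 derives one matching variable: emergent events are "categorized as occurring during the period of 21 days following the last vaccination based on the start date". The rule for placing events is "The assignment to time intervals will be done by day of onset and not by days ongoing/persisting", and the layout is "These summaries will be presented by the vaccination group", meaning the vaccine arm rather than the first or second injection.

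For solicited events, SAP 13.2 calls for summaries by vaccination and, where applicable, "combined across the two vaccinations using the solicited safety set". SAP 16 declares no change to the planned analysis. SAP 17 leaves the table list for later.

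**The concern.** The endpoint is worded for each dose, while the analysis is specified for the two-dose course as a whole. Followed to the letter, the SAP yields one percentage per arm where the endpoint, on its natural reading, asks for two. This is a two-dose study of antigen and adjuvant content, so a reader of the report would expect to see whether unsolicited events follow the first or the second injection, and in what share of the children who received that injection. As specified, the unsolicited tables show neither.

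**Working it through.** **Inputs**

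- Dose 2 is scheduled at Visit 1 + 21 days, with a window of -1 to +7 (time and events table in both documents). It therefore falls between Day 21 and Day 29.
- The treatment period ends on Day 43, stated to be 21 days after the second injection (SAP 3).
- The endpoint window is 21 days after each dose (Protocol 8.1.1.1).
- The unsolicited safety set is drawn from children with at least one dose (SAP 7.2 and 7.5).
- No unsolicited-event rates and no count of late attenders appear in the documents.

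**1. Reproduce the plan's own figure.** Dose 1 is on Day 1. Dose 2 is on Day 1 + 21 = Day 22. The window ends on Day 22 + 21 = Day 43, as stated. SAP 8.7, in its medication definitions, also equates Day 1 to 43 with 21 days after the last study vaccination. So for a child who completes both doses, the last vaccination is dose 2.

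**2. Compare the windows.** With dose 2 on Day d, the dose-1 window is Day 1 to Day 22, the dose-2 window is Day d to Day d + 21, and the pooled window is Day 1 to Day d + 21. For d of 23 or later, the full days inside the pooled window but outside both 21-day windows number d - 23.

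| Dose 2 given on | Pooled window | Days in both 21-day windows | Full days in neither |
|---|---|---|---|
| Day 21 | 1 to 42 | 21, 22 | none |
| Day 22 | 1 to 43 | 22 | none |
| Day 25 | 1 to 46 | none | 23, 24 |
| Day 29 | 1 to 50 | none | 23 to 28 |

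At the late edge the gap is 29 - 23 = 6 full days, or 6/21 = 29% of a 21-day window, plus the part of Day 29 before the injection. At the early edge and on the nominal day the windows share days, and the SAP has no rule for assigning such an event to a dose.

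**3. Can per-dose percentages be recovered from the pooled one?** Let p1 and p2 be the per-dose percentages among children who received both doses, with no events in the gap. If events after the two doses are independent, pooled = 1 - (1 - p1)(1 - p2). The rates below are assumed for illustration.

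- 20% and 12%: 1 - 0.80 × 0.88 = 29.6%. Swapping the doses also gives 29.6%.
- 30% and 10%: 1 - 0.70 × 0.90 = 37%. Swapping the doses also gives 37%.

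Without independence, the pooled value can lie anywhere from the larger of p1 and p2 up to p1 + p2. For 20% and 20% that range is 20% to 40%. The pooled percentage does not determine the pair.

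**4. Denominator.** For a child who stops after dose 1, the last vaccination is dose 1, so the window covers 21 days. A child with both doses contributes 21 + 21 = 42 days on the nominal schedule and 28 + 21 = 49 days at the late edge. All of them enter the same percentage.

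**5. How the SAP treats the other safety data**

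| Item | Split by first and second vaccination? |
|---|---|
| Extent of exposure (SAP 13.1) | Yes |
| Diary completeness (SAP 13.1.1) | Yes |
| Solicited events (SAP 13.2) | Yes, and combined where applicable |
| Unsolicited events (SAP 13.3) | No |

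The solicited endpoint in Protocol 8.1.1.1 is also framed by each vaccination, and there the SAP reads it as a per-dose quantity.

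**The case against.** The best defence is that the endpoint can be read as an event within 21 days of either dose. On that reading the pooled table matches it on the nominal schedule and is too wide only when dose 2 is late. Protocol 8.4.2.1.3 supports this view to a degree: it requests unsolicited summaries by vaccination group and says nothing of a split by dose, so the SAP follows the protocol's own analysis section. This stands, and it makes the ambiguity partly the protocol's. It does not remove the endpoint wording, and SAP 13.2 resolves the parallel solicited wording the other way.

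Other limits also stand:

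- A reader might infer that the primary endpoint is never computed, or that the information is lost. The documents do not support that. Onset dates are collected, all events are listed by child, and the table shells are still to come. The gap lies in the specification.
- A reader might infer that formulations cannot be compared. Each arm receives the same formulation twice, so the pooled percentage still compares two-dose regimens, and dose-specific reactogenicity is reported through solicited events. The study is descriptive, with no safety success criterion that depends on a per-dose rate.
- A reader might infer that dose-2 denominators are missing throughout. They are missing only for unsolicited events.
- A reader might take the late-visit gap as 7/21 = 33%. That is an upper bound, since the seventh day counts only up to the injection.

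**Conclusion.** The point holds as a mismatch between the stated endpoint and the specified analysis. The SAP defines no summary of unsolicited events by dose and no denominator of dose-2 recipients for them, and SAP 16 does not declare this as a departure. The pooled window equals the union of the two endpoint windows when dose 2 is on schedule. It exceeds that union by up to six full days, plus part of a seventh, at the late edge of the visit window. Whatever the schedule, it cannot supply per-dose percentages.

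This rests on reading the endpoint as one percentage per dose, which is the natural reading and the one the SAP applies to solicited events. The effect on any arm's percentage cannot be sized, because neither event rates nor the number of late or one-dose children is given; the percentages in the working are illustrations only.

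**What to change.** In SAP 8.7, derive two onset flags: 0 to 21 days after dose 1 and before dose 2, and 0 to 21 days after dose 2. State rules for:

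- events starting on the day of dose 2, including those whose timing relative to the injection is unknown;
- missing or partial onset dates, which SAP 8.7 now counts as inside the single window and which must not fall into both new windows by default;
- onset more than 21 days after dose 1 but before dose 2.

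In SAP 13.3, add per-vaccination tables of unsolicited events (any, by maximum severity, related) by formulation, overall and by age cohort. The denominator should be children in the unsolicited safety set who received that dose. Keep the pooled table, labelled *any vaccination*.

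The cost is SAP wording, two derived variables and a few extra tables. No new data are needed.

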13.4 Clinical Safety Laboratory Investigations

Not applicable

13.5 Concomitant Medication

Medications and vaccines taken prior or during the study are categorized as prior and/or concomitant. In addition, a subset of concomitant medications is defined for the period Day 1 to 43 (see [section 8.7](#) for definition).

Medications (generic drug name) will be coded using the WHODRUG dictionary.

The frequencies and percentages of subjects reporting prior, concomitant medications (Day 1 – 43 and Day to end of study) will be tabulated by vaccine group.

Statistical Analysis Plan, Protocol Number V87_30

06 MAY 2022 Final Version 1.0

14. INTERIM ANALYSIS

There are no planned interim analyses for this study.

15. DATA MONITORING COMMITTEES

Not applicable

16. CHANGES TO PLANNED ANALYSIS

Not applicable.

17. LIST OF FINAL REPORT TABLES, LISTINGS AND FIGURES

This list of tables will be defined later combined with the table's shells.

